12 weeks of at-home combined physical exercise and cognitive training intervention, consisting of six in-person visits for cognitive training and six telemedicine visits for physical exercise. At 3-month follow-up, the ICU survivors in the active treatment arm tolerated the combined program and had significantly better cognition as measured by the TOWER test, which is a timed objective measure of executive function (median score: 13.0 vs. 7.5, p<0.01) and functional score as measured by the Functional Assessment Questionnaire (median score: 1.0 vs. 8.0, p=0.04). The findings of this study are promising and provide rationale for our proposed trial. However, the study did not control for attention, had a very small sample size with no power to investigate the impact of the intervention on physical performance and it neither measured the ICU survivors overall quality of life nor their depressive and anxiety symptoms. Also, the isolated effects of physical rehabilitation or cognitive therapy on neuropsychiatric outcomes cannot be evaluated, as both interventions were concurrently administered.

Based on the background above, physical exercise and cognitive training hold promise for improving cognitive outcomes of ICU survivors although the current evidence is limited. We plan to further explore these findings through an efficacy, randomized, 2x2 factorial design clinical trial with four treatment arms, a) physical exercise and cognitive training, b) physical exercise, c) cognitive training, and d) attention control. The trial will not only be able to answer the question whether combined physical and cognitive therapies are superior to either of them alone as compared to attention control, but will also shed light on mechanisms of action of the intervention through use of serum biomarkers. An advanced mechanistic understanding of cognitive recovery after delirium will lead to refined interventions to prevent progression to dementia and Alzheimer's disease.

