Our team is proposing a 2x2 factorial design randomized controlled trial (RCT) called "Decreasing Alzheimer's Disease and Related Dementias after Delirium-Exercise and Cognitive Training (DDD-ECT)" to evaluate the efficacy of 12 weeks of combined physical exercise and cognitive training on the primary outcome of cognitive function among older ICU survivors who experienced delirium or subsyndromal delirium during their ICU stay. We propose to deliver these interventions via a facilitator-led, small group format using internet-enabled, multiparty-videoconference delivered directly into the participants' homes to achieve the following aims:

**Primary Specific Aim: Determine the effect of the combined physical exercise and cognitive training on the cognitive function of ICU survivors aged 50 and older.** Hypothesis: In comparison to older ICU survivors randomized to attention control or either intervention alone, those randomized to 12 weeks of combined physical exercise and cognitive training will have higher total index cognitive scores as assessed by the Repeatable Battery for the Assessment of Neuropsychological Status (RBANS) at 3 and 6 months post randomization.

**Secondary Specific Aim 1: Determine the effect of the combined physical exercise and cognitive training on physical performance, anxiety and depressive symptoms, and quality of life of ICU survivors aged 65 and older.** Hypotheses: In comparison to older ICU survivors randomized to attention control or either intervention alone, those randomized to 12 weeks of combined physical exercise and cognitive training will have higher physical performance as measured by short physical performance battery (SPPB) and two-minute step test, lower mood and anxiety symptoms as measured by Patient Health Questionnaire (PHQ-9) and Generalized Anxiety Disorder (GAD-7) scale, and higher quality of life as measured by the Medical Outcomes Study 36-item short form (SF-36) at 3 and 6-months post randomization.

**Exploratory Aim 1: To examine the mechanisms of action of combined training.** Hypothesis: At the completion of treatment, the combined intervention group will show reduced serum levels of CRP, IL-1, IL-6, IL-8, TNF- $\alpha$ , S-100 $\beta$ , and GFAP and increased levels of BDNF, VEGF, and IGF-1 compared to the attention control, or either intervention alone groups.

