## 8. Statistical Considerations

To verify the comparability of the randomized groups, patients' baseline characteristics among the four groups will be compared using analysis of covariance (ANCOVA) for continuous variables and the Cochran-Mantel-Hansel statistic for categorical variables while adjusting for age group. We will examine the distributions of continuous variables and use alternative approaches such as transformation or nonparametric methods in cases of violation to the normal distribution assumption. We will also examine the frequency distribution of all categorical variables and adopt exact inference procedures in cases of zero or small cell size. All analyses will be conducted using the SAS 9.4 (SAS Institute, Carey, North Carolina).

**Primary Specific Aim:** Mixed effects models will be used with repeated RBANS scores collected at baseline, 3 months and 6 months as the outcome measures, group, time and a group by time interaction as independent variables while adjusting for stratification variables and other potential baseline covariates found to be significantly different in univariate comparisons. A significant interaction between group and time would indicate differences in changes of cognitive functions over time among the four groups. Post-hoc comparisons will be conducted following a significant interaction between group and time to compare the effect of the combined training group to the other three groups (attention control, cognitive training only, and exercise only groups) at 3 month for immediate training effect and at 6 month for sustained training effect. Separate mixed effect models will also be used for repeated, Trail Making A&B, and Stroop Color and Word Test scores.

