**Secondary Specific Aim 1:** Separate mixed effects models will be used with repeated measures (SPPB, 2-minutes step, PHQ-9, GAD-7, SF-36 PCS and MCS) as the outcome variables, group, time and interactions between group and time as independent variables while adjusting for stratification variables and other baseline covariates that may be different among the four groups. Significant interactions between group and time in these models would indicate differences in changes of functional outcomes, depressive symptoms, and anxiety levels or quality of life over time among the four groups. Post-hoc analyses will also be conducted following significant interactions in the mixed effects models to compare the combined training group to the other three groups and to determine how early a group difference can be detected and whether the effect extends beyond the training period.

**Exploratory Aim 1:** Changes in the serum levels of CRP, IL-1, IL-6, IL-8, TNF-  $\alpha$ , S-100 $\beta$ , GFAP, BDNF, VEGF, and IGF-1 will be calculated and used as the dependent variables in ANCOVA models with group as the independent variable and adjusting for stratification variables and baseline covariates that are

found to be different among the groups in univariate comparisons. Post-hoc comparisons will be used following a significant group effect to compare biomarker levels in the combined training group to the other three groups.

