Sample Size and Power: Cognitive training had been found to have a moderate effect size of approximately 0.5 SD and the combined training was found to have a larger effect size of 0.9 SD when comparing to the control group in healthy elderly subjects. Assuming effect sizes of 0.4 SD in the cognitive training only group and the exercise only groups at 3 and 6 month post baseline compared to the attention control group and effect size of 0.8 SD in the combined training group at 3 and 6 month post baseline compared to the attention group, a sample size of 60 patients in each group will yield 83% power at detecting a significant group by time interaction in a mixed effect model adjusting for correlations of 0.2 for outcomes measured 3 month apart and correlations of 0.1 for outcomes measured 6 month apart at  $\alpha=0.05$ . The power estimation was conducted using the GLMPower procedure in SAS. To further assume that 30% patients may miss some post-baseline assessments, we will need to enroll a total of 344 patients into the study (86 patients per group). Outcomes in Secondary Aim 1 will also have 83% power to detect effect sizes similar to those described for the Primary Aim. For Secondary Aim 2, we will have 81.7% power to detect an overall treatment effect in changes in biomarkers with effect sizes of 0.31 SD in the cognitive training only and the exercise only groups and 0.62 SD in the combined training groups at  $\alpha=0.05$  using one-way ANOVA and the Power procedure in SAS.

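### The 83% power belongs to the overall group-by-time test; combined training against each single intervention has 41–61% at 3 months with 60 per arm, and no rule says which contrasts and visits must succeed

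*Combined protocol and SAP*

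**What the plan says.** The primary hypothesis in Section 2 sets combined training against participants "randomized to attention control or either intervention alone", on the RBANS total index at 3 and 6 months. Section 1 says the trial will be able to "answer the question whether combined physical and cognitive therapies are superior to either of them alone".

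The Primary Specific Aim paragraph of Section 8 fits a mixed model to RBANS at baseline, 3 and 6 months with a group-by-time interaction. It then says: "Post-hoc comparisons will be conducted following a significant interaction between group and time". The comparisons are combined against each of the other three arms, "at 3 month for immediate training effect and at 6 month for sustained training effect". Secondary Specific Aim 1 has the same structure, with contrasts run "following significant interactions in the mixed effects models to compare the combined training group to the other three groups".

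The sample-size paragraph gives one power figure for the primary aim: 60 per arm "will yield 83% power at detecting a significant group by time interaction in a mixed effect model". It inflates to 86 per arm because "30% patients may miss some post-baseline assessments", and adds: "Outcomes in Secondary Aim 1 will also have 83% power to detect effect sizes similar to those described for the Primary Aim".

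**The concern.** The interaction test asks whether the four arms change differently in any way. It can be significant because any training beats none. The hypothesis and the stated purpose of the trial are narrower: that combining the two interventions adds something over each alone. That claim rests on the contrasts of combined with each single arm, where the assumed difference is half that against control.

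Two things are therefore missing. The power of the contrasts that carry the claim is not given. Nor does any section say which of the six comparisons (three comparators at two visits) must be significant, or at what alpha, for the primary aim to be met. The trial could pass its only powered test and still be unable to separate combined training from its parts, and the comparisons to emphasise could be chosen after the results are seen.

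**Working it through.** **Inputs (Section 8, sample-size paragraph).** Effects against control at 3 and 6 months: 0.4 SD for each single arm, 0.8 SD for combined. Correlations: 0.2 for scores 3 months apart, 0.1 for scores 6 months apart. 60 evaluable per arm; alpha 0.05. Allowing for 30%: 60/0.7 = 85.7, so 86 per arm and 344 in total. *Assumed, because not stated:* two-sided 0.05 for each contrast.

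**1. The plan's own figure.** For changes from baseline (SD 1), the variances are 2(1−0.2) = 1.6 at 3 months and 2(1−0.1) = 1.8 at 6 months, and the covariance is 1 − 0.2 − 0.1 + 0.2 = 0.9. The arm effects 0, 0.4, 0.4, 0.8 have mean 0.4 and squared deviations summing to 0.32. The entries of the inverse covariance matrix sum to (1.6 + 1.8 − 2×0.9)/(1.6×1.8 − 0.9²) = 1.6/2.07 = 0.773. The noncentrality is 60 × 0.32 × 0.773 = 14.84 on (4−1)(3−1) = 6 df. Power is 83.8% (chi-square) or 83.0% (Hotelling-Lawley F). The stated 83% is confirmed.

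**2. Combined against one single arm, 3 months.** The difference is 0.8 − 0.4 = 0.4 SD, with SE = √(2v/n) and a noncentral t on 4(n−1) df. The variance v depends on the contrast, which the plan does not specify: 2(1−0.2) = 1.6 for change, 1 for visit means, 1 − 0.2² = 0.96 with baseline adjustment. At n = 60 the SEs are 0.231, 0.183 and 0.179, so 0.4/SE is 1.73, 2.19 and 2.24 against a critical value of 1.97.

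| Observed per arm | Change | Visit mean | Baseline-adjusted |
|---|---|---|---|
| 60 | 41% | 59% | 61% |
| 73 | 48% | 67% | 69% |
| 86 | 54% | 74% | 76% |

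The 73 row assumes that the 30% each miss one of the two visits, split evenly: 86 × 0.85 = 73. The 86 row assumes nothing is missing. At 6 months with 60 per arm the range is 37–59%.

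**3. Combined against control, 3 months, 60 per arm.** With 0.8 SD the power is 93%, 99% and 99%.

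**4. With the plan's gate (simulated arm means, 60 per arm; change, visit mean, adjusted).** Significant interaction and one given single arm beaten at 3 months: 38, 51 and 53%. Significant interaction but neither single arm beaten at 3 months: 31, 19 and 17%.

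**5. If combining adds nothing.** Let all three active arms have 0.8 SD. The squared deviations from the mean of 0.6 sum to 0.36 + 3×0.04 = 0.48. The noncentrality is 60 × 0.48 × 0.773 = 22.3, and the gate passes about 96% of the time. Among trials that pass, the four unadjusted combined-against-single tests (two arms, two visits) give at least one false difference in about 16–17%, and one that falsely favours combined in about 8–9%.

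**6. Sensitivity to the correlation (assumed values; single-arm contrast, 3 months, 60 per arm; change, visit mean, adjusted).** At 0.5: 59, 59 and 71%. At 0.7: 80, 59 and 86%.

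**The case against.** The strongest defence is that the plan misstates nothing. The 83% is attached to the interaction by name, and an omnibus test followed by contrasts is a recognised strategy. That stands. A reader might infer that the power calculation is wrong or mislabelled; it is neither.

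A reader might also infer that there is no decision structure at all. The documents do not support that: Section 8 sets a gate and names three contrasts at two visits. What is absent is the rule on which must succeed and at what alpha.

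The 41% is the least favourable reading. The plan's wording can equally mean visit means, which gives 59%. The mixed model also keeps partial data, so 60 per arm is pessimistic and about 73 is closer under the pattern assumed above. Both points stand, but no entry in the table reaches 83%.

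The correlations drive the result. At an assumed 0.7 the shortfall largely disappears for change and adjusted contrasts, though not for visit means. But 0.2 and 0.1 are the plan's own values, which is a reason to report contrast power together with the correlation.

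Finally, the design is a 2×2 factorial with additive planned effects. Each marginal effect, 120 against 120, would have 68% (change) to 88% (adjusted) power at 3 months. That is a legitimate option, but it is not the planned analysis, and it shows that combined beats a single arm only if the effects are additive.

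**Conclusion.** The point holds in this form. The 83% is sound for the omnibus interaction, but the contrasts that distinguish combined training from its components have about 41–61% power at 3 months with 60 per arm, and 54–76% even with all 86 observed. The shortfall is confined to combined against each single arm; combined against control is well powered. The undefined rule for success is a separate gap and does not depend on any power assumption.

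The figures assume the plan's effects and correlations and a two-sided 0.05 test of each contrast. A reader might go further and conclude that the trial as a whole is underpowered, or that it must enrol more patients. The documents do not support that: the result depends on the correlation and the type of contrast, and the hypothesis does not say whether all three comparators must be beaten at both visits.

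The Secondary Aim 1 power sentence needs the same qualification, because it carries over the same omnibus figure to the same kind of contrasts.

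**What to change.** In Section 8:

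1. State that the 83% applies to the interaction only, both for the primary aim and in the Secondary Aim 1 sentence. Report the power of each combined-against-other contrast, with the correlation and contrast type assumed.
2. Prespecify the three combined-against-other contrasts as the tests of the primary hypothesis. Name the deciding visit or visits and the rule: either all three at 0.05 each, or any of them with an adjusted alpha and a conclusion limited to the comparators beaten.
3. Estimate the contrasts with baseline adjustment in the existing mixed model (baseline means constrained equal across arms).

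The cost is SAP wording and a restated power paragraph; no extra patients, visits or data are needed. Step 3 gains about 20 points over a change contrast (41% to 61%) but only about 2 over visit means (59% to 61%). It does not restore 83%, so the remaining shortfall should be disclosed.

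Optional trade-offs, not requirements:
- Keeping or dropping the omnibus gate. At 60 per arm it costs up to about 8 points of single-arm power.
- Averaging the 3- and 6-month scores. This gives about 82% adjusted, 80% as visit means and 48% as change, and only if the effect is equal at both visits.
- Reporting factorial marginal effects, with the additivity assumption stated.

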### **Randomization:**

[figure not shown]
After obtaining an informed consent, study staff will complete a baseline assessment consisting of measures of cognition, physical function, depression and anxiety, and quality of life (see measures section 4.3.l. below). Blood samples will also be collected from the participants at the time of baseline assessment. Baseline may be completed at subject's home after hospital discharge if unable to complete full assessment in the hospital. After initial assessment, study subjects will be randomized to study groups. Randomization will be stratified by discharge location (home, other facility) and managed by the IU site

[During COVID-19 health crisis, baseline assessments will be completed via phone; abbreviated measures of cognition, and no measures of physical function will be obtained due to the limitations of phone administration. Blood samples will not be collected.]

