## 9. Outcome Measures

[During COVID-19 health crisis, outcomes assessments will be completed via phone; abbreviated measures of cognition, and no measures of physical function will be obtained due to the limitations of phone administration. Blood samples will not be collected.]

**Cognitive Outcome Measures:** The Repeatable Battery for the Assessment of Neuropsychological Status (RBANS) total index score will provide the primary outcome for the trial. Secondary outcomes will be assessed using individual neuropsychological tests of processing speed, executive control, and new learning ability as follows: Trail Making Test Parts A and B (seconds to complete), and Stroop Color and Word Test (interference trial). These measures sample major domains of cognition affected in ICU survivors.

**Physical Performance and Cardiovascular fitness:** Physical training effects on balance and strength will be assessed via the Short Physical Performance Battery (SPPB), a validated objective assessment. The SPPB yields a performance score of 0-12 (0-4 poor, 5-7 intermediate, 8-12 good). A difference of 1 point indicates a significant change in function. Physical training effects on cardiovascular fitness will be assessed via the 2-minute step test. We have selected the 2-minute step test for cardiovascular fitness because it is a validated measure of aerobic capacity, does not require equipment, and can be used in the home setting. Grip strength with dominant hand will also be measured.

**Self-reported Mood and Anxiety symptoms:** We will use the Patient Health Questionnaire–9 (PHQ-9) and Generalized Anxiety Disorder Scale (GAD-7) to determine the impact of the intervention on ICU's survivors' mood and anxiety. The PHQ-9 is a nine-item depression scale with a total score from 0 to 27 and the GAD-7 is a seven-item anxiety scale with a total score from 0 to 21. Both of these scales are derived from the Patient Health Questionnaire, have good internal consistency, and test-retest reliability as well as convergent, construct, criterion, procedural and factorial validity for the diagnosis of major depression and general anxiety disorder.

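### The biomarker change-score analysis drops patients with one blood sample and names no baseline-marker adjustment, although blood collection is suspended under COVID-19; the 81.7% power does not state its 60-pair condition

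*Combined protocol and SAP*

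**What the plan says.** Section 8, Exploratory Aim 1, takes the change in each of ten serum markers. These changes "will be calculated and used as the dependent variables in ANCOVA models", with arm as the factor. Adjustment is for the stratification variables and for baseline covariates that turn out to differ between arms. Section 9 provides two sampling times only, baseline and 3 months.

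Section 8, Sample Size and Power, says of the biomarkers "we will have 81.7% power to detect an overall treatment effect in changes in biomarkers", for "effect sizes of 0.31 SD in the cognitive training only and the exercise only groups and 0.62 SD in the combined training groups", obtained "using one-way ANOVA and the Power procedure in SAS". It attaches no number of patients to that sentence. The numbers stand earlier in the same paragraph, for the primary outcome: "a sample size of 60 patients in each group will yield 83% power", and then, assuming that "30% patients may miss some post-baseline assessments, we will need to enroll a total of 344 patients into the study (86 patients per group").

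The COVID-19 text in section 4 (Randomization) says of baseline: "Blood samples will not be collected". Section 5 (Outcomes Assessments) and section 9 carry the same rule for follow-up: "no measures of physical function will be obtained due to the limitations of phone administration. Blood samples will not be collected". The biomarker analysis and its power statement make no reference to this suspension.

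**The concern.** Two features of the plan interact. The outcome can be formed only from a pair of samples, and the COVID-19 rules can remove either member of the pair. A patient enrolled by phone during the restrictions has no baseline blood. If in-person visits have resumed by 3 months, that patient can give a 3-month sample, but the main analysis cannot use it.

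The analysis is also less efficient than it need be for patients who have both samples. The baseline marker value enters the model only if it happens to count among the covariates found to differ between arms. Otherwise the analysis is of unadjusted change.

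Finally, a reader of the power statement cannot tell that 81.7% depends on a particular number of complete pairs, or that the loss allowance was written for missed post-baseline assessments and not for a missing baseline sample. At stake are precision on an exploratory mechanistic aim and the use of blood already drawn.

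**Working it through.** **Inputs.** From section 8: effect sizes 0.31, 0.31 and 0.62 SD, alpha 0.05, one-way ANOVA, four equal arms, 60 evaluable and 86 enrolled per arm, 30% loss. Assumed: the control mean is 0, and the SD is that of the change (the sentence does not say). Not in the documents: the number of patients affected by the suspension, and the baseline-to-3-month correlation r of the markers.

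**1. The plan's figure.** The non-centrality is λ = n × Σ(μᵢ − μ̄)². With means 0, 0.31, 0.31 and 0.62 the average is 0.31, so the sum is 2 × 0.31² = 0.1922.

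- n = 60: λ = 60 × 0.1922 = 11.53, df 3 and 4 × 59 = 236, power 0.8170. This matches the plan exactly.
- n = 86: λ = 86 × 0.1922 = 16.53, df 3 and 340, power 0.9391. No match.

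The enrolment figure also reproduces: 60 / 0.70 = 85.7, so 86 per arm and 344 in total. The 81.7% is therefore the power with 60 pairs per arm, after the 30% loss has been taken off.

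**2. Power by number of complete pairs per arm (unadjusted change-score ANOVA only).**

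| Pairs per arm | Power |
|---|---|
| 86 | 93.9% |
| 68.8 (20% loss from 86) | 87.2% |
| 60 | 81.7% |
| 58 | 80.2% |
| 57 | 79.5% |
| 54 | 77.0% |
| 50 | 73.3% |
| 40 | 62.3% |

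About 86 − 60 = 26 pairs per arm can be lost, from all causes, before power drops below 81.7%.

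**3. What baseline adjustment gains for a pair.** Take equal variances at the two visits, set to 1, and the same absolute effect. The residual variance of an unadjusted change is 2(1 − r). With baseline adjustment it is 1 − r². The ratio is 2(1 − r)/(1 − r²) = 2/(1 + r).

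| r (assumed) | 2(1 − r) | 1 − r² | Gain in information |
|---|---|---|---|
| 0.2 | 1.60 | 0.96 | 1.67 |
| 0.4 | 1.20 | 0.84 | 1.43 |
| 0.6 | 0.80 | 0.64 | 1.25 |

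The value 0.2 is the plan's own assumption for primary outcomes measured 3 months apart; nothing in the documents gives r for the markers. Ignoring the small effect of error df, an adjusted analysis would reach about 81.7% with 60 × (1 + r)/2 pairs per arm: 36, 42 and 48 at these three values. The table in step 2 therefore does not describe the adjusted analysis.

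**4. What a 3-month-only sample is worth.** Its variance is 1, against 1 − r² for a baseline-adjusted pair. It therefore carries 96%, 84% or 64% of the information of such a pair at r = 0.2, 0.4 and 0.6. The change-score analysis uses none of it.

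**5. How many such patients.** This cannot be known from the documents. As a rough guide, they are the patients enrolled in about the three months before in-person work resumes. With uniform enrolment of 86 per arm over 3 to 5 years (assumed; section 11 calls this a five-year study), that is 86 × 3/60 = 4.3 to 86 × 3/36 = 7.2 per arm for each reopening, before dropout.

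**The case against.** **No shortfall is shown.** A reader might infer that the 81.7% is unsupported, or that the plan has no slack. The documents do not bear that out. They enrol 86 per arm, the figure is already net of 30% loss, and the number of patients in the suspension is not given. A 3-month draw missed under the COVID-19 rule is itself a missed post-baseline assessment, which the 30% covers. What remains is narrower: a missing baseline sample falls outside the wording of that allowance, and the Missing Data paragraph foresees only death and withdrawal.

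**Single samples need not be wasted altogether.** A reader might infer that these patients are lost to the trial. The Missing Data paragraph plans imputation or full-likelihood sensitivity analyses, which could use them. It does not say that these extend to the biomarkers, and its missing-at-random argument rests on mixed models, which the biomarker aim does not use. So the patients drop out of the main analysis; more than that cannot be claimed.

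**The 3-month draw is already planned.** Section 9 schedules it, the suspension is limited to the crisis, and nothing makes it conditional on a baseline draw. This stands, and no new rule on drawing blood is needed.

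**The aim carries little weight.** Sections 2 and 8 label it exploratory, and the 344 comes from the primary outcome alone. This also stands, although the power paragraph and section 9 still number it as a second secondary aim. It limits the importance of the point without removing it, since the plan does state a power for this aim.

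**Few patients may be recovered.** Agreed. Most of the likely benefit is in the baseline adjustment of complete pairs.

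**Conclusion.** The point holds as a minor, inexpensive improvement. The main biomarker analysis needs both samples, names no baseline-marker adjustment, and sits beside rules that suspend blood collection at either visit. Adjusting pairs for baseline raises the information per pair by a factor of 1.25 to 1.67 for r from 0.6 down to 0.2, given equal visit variances and an assumed r. The number of 3-month-only samples recovered may be small.

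The 81.7% is arithmetically correct, but it is conditional on 60 complete pairs per arm and makes no separate allowance for suspended collection. Power would fall below 80% at 57 pairs. Whether the trial ends above or below 60 cannot be judged from the documents.

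**What to change.** **Section 8, Exploratory Aim 1.** Replace the change-score ANCOVA with a likelihood model of both marker visits: one common mean across arms before randomisation, separate arm means at 3 months, a free covariance between visits, and adjustment for the stratification variable (discharge location). The treatment effect is the arm difference at 3 months. Patients with only a 3-month sample then contribute, and pairs are adjusted for baseline whether or not the arms happen to differ.

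**Section 8, Sample Size and Power.** Add that 81.7% is the power of the unadjusted change-score ANOVA with 60 complete pairs per arm, already net of the 30% loss from 86, and that suspended blood collection has no separate allowance. Give the power at other numbers of pairs (86: 93.9%; 54: 77.0%; 50: 73.3%; 40: 62.3%), labelled as applying to that analysis and not to the new model. Use one label for the aim throughout.

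**Cost.** Analysis-plan wording and a little programming; no extra patients, visits or blood. The model assumes that missing baseline samples are unrelated to arm. That is reasonable, because section 4 places the baseline draw before randomisation. Samples missing at 3 months still need the missing-at-random assumption.
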